5.6. LV VECTORS AND PACING CONFIGURATIONS

The 14 LV vectors considered in this study are:

Table 2: LV tests

#	IS1 lead	IS4 lead
1	LVtip-LVring	LVtip1-LV2
2	LVtip-RVring	LVtip1-RVring
3	LVtip-RVcoil	LVtip1-RVcoil
4	LVtip-CAN	LVtip1-CAN
5	LVring-RVcoil	LV2-RVcoil
6	LVring-CAN	LV2-CAN
7		LVtip1-LV4
8		LV2-LV4
9		LV3-LV2
10		LV3-LV4
11		LV3-RVring
12		LV3-RVcoil
13		LV3-CAN
14		LV4-RVcoil

LEVEA – Statistical Analysis Plan

Three LV pacing configurations are considered in this study to perform “In-Clinic LVAT” tests for all eligible LV pacing vectors:

- DDD A-test (atrium overdrive)
- DDD P-test (no atrium overdrive)
- VVI test

5.7. LV VECTOR TEST

“In-Clinic LVAT” test is composed of several LV Vector Tests, each corresponding to a selected LV pacing vector (out of a possible 14 LV vectors).

The following definitions apply when performed on the same subject, with the same pulse width (in order to be comparable, the pacing width between automatic tests (any of them) and manual test needs to be strictly similar), on the same LV pacing vector and at the same visit:

- Attempted LV Vector test: If a LV Vector test, corresponding to an available LV pacing vector, was not launched during a visit then the LV Vector test will be classified as “Not Attempted”, and otherwise “Attempted”. That is, if an LV Vector test which was launched and neither interrupted nor aborted, it will be considered as “Attempted”.
- A complete LV Vector Test: test was performed (not aborted or interrupted) and a threshold value is provided by the algorithm. A LV Vector test resulting to a “no capture or high pacing threshold > 5V” at starting amplitude is considered as a complete LV Vector test. If a test was not aborted/neither interrupted and has no value, then the test will be considered as attempted but not completed.

The conditions for Attempted, Aborted and Interrupted can be further understood from the following table:

Table 3: Conditions for Completed LV test

Attempted	Aborted = Yes or No	Interrupted = Yes or No	Complete	Threshold Value
No	NA*			
Yes	Yes	No	No	Missing
Yes	No	Yes	No	Missing
Yes	No	No	Yes	Not missing

* Corresponding data is missing.

- A successful LV Vector Test: threshold value provided automatically by the algorithm is equivalent to the manual threshold test done by the physician among the complete LV Vector Tests.

LEVEA – Statistical Analysis Plan

An LV threshold value obtained from the device algorithm (automatic) will be considered as equivalent to the manual threshold value if the automatic and manual LV threshold tests has the same value, with the same pacing pulse width, with a flexibility of ± 2 steps (meaning $\pm 0.5V$ if threshold $< 2.5V$, else $\pm 1V$). A margin of ± 2 steps is accepted because of the variability of the threshold, and due to the design of the algorithm.

The equivalent range for the Algorithm for a Manual threshold is provided in the table below:

Table 4: Equivalent ranges for Successful LV tests (Manual vs. Algorithm)

Manual Threshold value obtained (in V)	Equivalent Range of the Algorithm (Automatic threshold) (in V)
7	>5
6	>5
5	>4.0
4.5	3.5-5.0
4.0	3.0-5.0
3.5	2.5 - 4.5
3.0	2.25 - 4.0
2.75	2.25 -3.5
2.5	2- 3.5
2.25	1.75-3
2.0	1.5-2.5
1.75	1.25-2.25
1.5	1.0-2.0
1.25	0.75-1.75
1	0.5-1.5
0.75	0.25-1.25
0.5	0.25-1.0

LEVEA – Statistical Analysis Plan

0.25	0.25-0.75
------	-----------

Note: if an LV test is reported to be done, but no manual threshold value is present, it will be imputed as “Missing”.

- A failed LV Vector Test: threshold value provided automatically by the algorithm is not equivalent to the manual threshold test done by the physician or adjudicated by the independent reviewer among the complete LV Vector Tests.

As values determined by the algorithm are not displayed on the programmer screen, data are stored in the electronic Real-Time Data (RTD) files that are loaded in the electronic Case Report Form (eCRF) in order to be extracted by the sponsor.

- Diagnostic accuracy is defined as an accurate adjudication by an independent reviewer of LV threshold value provided by the algorithm. The adjudication is based on capture and loss of capture analysis on electrogram strips recorded and stored during “In-Clinic LVAT” tests. The LV threshold value provided by the algorithm compared to the reviewer adjudication is considered accurate if the difference is within ± 1 step.

The “Accurate” range for the Independent Reviewer for a Algorithm (Automatic) threshold is provided in the table below:

Table 5: Equivalent ranges for Accurate LV tests
(Algorithm vs. Independent reviewer)

Threshold value obtained with the algorithm (Automatic) (in V)	Accurate Range (Independent reviewer)
>5	>5
5.0	>4.5
4.5	4.0-5.0
4.0	3.5-4.5
3.5	3.0-4.0
3.0	2.5-3.5
2.5	2.25- 3
2.25	2.0-2.5
2.0	1.75-2.25
1.75	1.5-2.0

LEVEA – Statistical Analysis Plan

1.5	1.25-1.75
1.25	1.0-1.5
1.0	0.75-1.25
0.75	0.5-1.0
0.5	0.25-0.75
0.25	0.25-0.5

- Assessment of LV pacing threshold underestimation: comparison to manual LV threshold value will be performed by comparing manual and automatic LV threshold values at each visit. An underestimated LV threshold value of “In-Clinic LVAT” feature is defined as a value result more than 2 steps below the LV threshold measured manually (meaning -0.5V if threshold<2.5V, else -1V as measured).

Table 6: Ranges for Under-estimated LV tests
(Manual vs. Algorithm)

Manual Threshold value obtained (in V)	Under-estimated if - Automatic threshold value (in V)
7	< 5
6	<4.5
5	< 4.0
4.5	<3.5
4.0	<3.0
3.5	<2.5
3.0	<2.25
2.75	<2.25
2.5	<2.0
2.25	<1.75
2.0	<1.5
1.75	<1.25

LEVEA – Statistical Analysis Plan

Manual Threshold value obtained (in V)	Under-estimated if - Automatic threshold value (in V)
1.5	<1.0
1.25	<0.75
1	<0.5
0.75	Not Applicable
0.5	Not Applicable
0.25	Not Applicable

Note: if an LV test is reported to be done, but no manual threshold value is present, it will be imputed as “Missing”.

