4.1.3. Secondary endpoints

a. Assessment of the diagnostic accuracy of “In-Clinic LVAT” test at M0 follow-up: Independent reviewer validation of LV threshold value provided by algorithm

This endpoint is the number of accurate determination of the pacing threshold value provided by the algorithm feature and an independent reviewer, on all LV pacing vectors and all pacing configurations available at M0 follow-up.

Diagnostic accuracy is defined as an adjudication of LV threshold value provided by the algorithm. The adjudication is based on capture and loss of capture analysis on electrogram strips recorded and stored during “In-Clinic LVAT” tests. The threshold value provided by the algorithm compared to the reviewer adjudication is considered accurate if the difference is within ± 1 step. The reason for incorrect determination of capture/loss of capture (if any) will be reported.

In case several LV Vector Tests were eligible with the same LV pacing vector, in the same pacing configuration, for the same subject, on the same follow-up, only the last one will be considered.

b. Assessment of the success rate of “In-Clinic LVAT” test at M0 follow-up: comparison to manual LV threshold tests results

This endpoint is the success rate of “In-Clinic LVAT” feature on pacing vectors and pacing configurations available at M0 follow-up. The method of analysis is similar to the primary endpoint.

c. Assessment of the success rate of “In-Clinic LVAT” test at M1 follow-up: comparison to manual LV threshold tests results

This endpoint is the success rate of “In-Clinic LVAT” feature on pacing vectors and pacing configurations available at M1 follow-up. The method of analysis is similar to the primary endpoint.

d. Evaluation of the applicability of the algorithm

The algorithm may not be applicable to some subjects, mainly because of a very long inter-ventricular conduction delay. A subject is defined as eligible as soon as one LV Vector Test is complete.

The endpoints for the applicability of the algorithm in the population are:

- The percentage of subjects who are eligible to receive the feature that is the percentage of subjects with at least one complete LV Vector Test at M0 and M1 follow-ups.
- The number of LV Vector Tests attempted, and percentage of completed and successful LV Vector Tests at M0 and M1 follow-ups per subject.

e. Assess the device characteristics in terms of safety and deficiencies

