For number of LV vector tests “completed”, the percentage will be calculated based on the number of LV vector tests attempted and for number of LV vector tests “accurate”, the percentage calculated based on number of Complete LV vector tests .

A heat plot will be presented for Attempted, Completed and Accurate percentages. If the percentage is > 90%, it will be coloured green, if the percentage is between 75% and 90% (inclusive), it will be coloured brown and if the percentage <75%, then it will be coloured orange.

This will also be listed.

For this analysis, EP will be used considering M0 visit only.

10.2. ASSESSMENT OF THE SUCCESS RATE OF “IN-CLINIC LVAT” TEST AT M0 VISIT: COMPARISON TO MANUAL LV THRESHOLD TESTS RESULTS

This endpoint is the success rate of “In-Clinic LVAT” feature on LV pacing vectors and LV pacing configurations available at M0 visit.

The threshold obtained from the “In-Clinic LVAT” feature, extracted from RTD files, will be compared against manual LV threshold values recorded in the eCRF. The definition of equivalence is same as that of primary analysis.

Test will be evaluated at different LV pacing configuration: DDD A-test, DDD P-test and VVI test. Among all the eligible complete LV Vector Tests collected, only those with a manual LV threshold test performed in the same conditions (same pacing pulse width) at M0 visit and reported in the electronic Case Report Form (eCRF) will be retained.

All analyses performed for this Secondary endpoint will be performed based on manual LV threshold tests results considering data only from M0 visit (except for testing of hypothesis and missing data imputation).

This Secondary endpoint will be based on M0-ITT population.

Decomposition of “In-Clinic LVAT” Success Rate by LV Vector and by LV pacing configuration at M0 visit

Only subjects with non-missing manual data will be considered.

Total number of attempted, completed and successful LV vector tests will be presented by LV vector for each LV pacing configuration.

For number of LV vector tests “attempted”, the percentage will be calculated based on the EP population.

For number of LV tests “completed”, the percentage will be calculated based on the number of LV vector tests attempted.

For number of LV vector tests “Successful”, the percentage will be calculated based on number of Complete LV vector tests.

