A heat plot will be presented for Attempted, Complete, Underestimated percentages. If the percentage is > 90%, it will be coloured green, if the percentage is between 75% and 90% (inclusive), it will be coloured brown and if the percentage <75%, then it will be coloured orange.

This Secondary endpoint will be based on EP population and will also be listed.

C. Analysis of Unexpected Function Operations

Number and percentage of unexpected function operations by analyzing EGM collected in the RTD files and ECG (from DDD A-test) performed during “In-Clinic LVAT” test at each visit will be presented.

- i. Number and percentage of LV vector tests with unexpected functions based on all LV vector tests attempted.
- ii. Number and percentage of LV vector tests with unexpected functions per LV vector per LV pacing configuration per visit

Total number of attempted, completed, with expected function, with unexpected function LV vector tests will be presented by LV vector for each LV pacing configuration by visit.

For the LV tests performed for subjects with either IS1 and IS4 leads six LV vectors common to IS1 and IS4), the percentage for the number of LV vector tests

LEVEA – Statistical Analysis Plan

“attempted”, will be calculated based on the number of subjects implanted with either IS1 and IS4 leads.

For the LV tests performed for patients with IS4 leads (eight LV vectors pertaining only to IS4), the percentage for the number of LV vector tests “attempted”, will be calculated based on the number of patients implanted with IS4 lead.

For number of LV vector tests “completed”, “with Unexpected Function” and “with Expected Function”, the percentage will be calculated based on the number of LV vector tests attempted .

The reasons for unexpected assessment at M0 visit, M1 visit and overall will be presented as table and listing. The missing reasons (if any) for unexpected assessment will be presented as “Not available”. For the table, the number and percentages of the reasons will be presented with the denominator of the percentages based on the total number of unexpected assessments.

All unexpected function operations will be listed.

This Secondary endpoint will be based on EP population.

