18. APPENDICES 2: ANALYSES DATASET SPECIFICATIONS

The Specification Document that describes the Analyses dataset variables is “LEVEA_Derivation_metadata.xls”.

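### SAP 10.2 and 10.3 divide attempted tests on IS4-only vectors by the whole evaluable population, and one sentence in SAP 5.7 misstates which tests count as attempted

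*SAP*

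**What the plan says.** **Denominators.** SAP Table 2 lists 14 vectors: six common to IS1 and IS4 leads, and eight on IS4 leads only. The 10.2 decomposition reports attempted, completed and successful tests by vector and configuration. It takes the attempted percentage on EP, without a split by lead, and considers only subjects with non-missing manual data. SAP 10.3 applies the same analysis at M1 and names EP for its decomposition. EP (SAP 6.2) contains both IS1 and IS4 subjects. For the eight IS4-only vectors, SAP 10.1, 11.1B, 11.1C and 13.5 use the number of patients or subjects with an IS4 lead. SAP 10.4 uses EP subjects with the respective lead and configuration.

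**Meaning of attempted.** SAP 5.7 says that a test which "was not launched during a visit then the LV Vector test will be classified as" Not Attempted, and that any other test is attempted. The next sentence, opening with *That is*, says "if an LV Vector test which was launched and neither interrupted nor aborted, it will be considered as" attempted. Table 3 contains the row "Yes Yes No No Missing" (attempted, aborted, not interrupted, not complete, no value) and a matching row for interrupted tests, also marked attempted. The text adds that if a test is neither aborted nor interrupted but has no value, "the test will be considered as attempted but not completed". Table 3 has no row for that class.

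**Use.** CIP 4.1.3d makes this a secondary endpoint: "The number of LV Vector Tests attempted, and percentage of completed and successful LV Vector Tests at M0 and M1 follow-ups per subject". CIP 4.1.1 defines complete, successful and failed tests, but not attempted ones. For completed tests in the SAP decompositions, "the percentage will be calculated based on the number of LV vector tests attempted". SAP 11.1C reports "Number and percentage of LV vector tests with unexpected functions based on all LV vector tests attempted".

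**The concern.** Attempted and completed percentages show how often the feature could be run and how often it returned a value.

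In 10.2 and 10.3, a low attempted percentage for an IS4-only vector could mean that IS4 subjects were not tested, or only that many subjects have IS1 leads. The heat plot colours both the same way.

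In 5.7, a programmer following the *That is* sentence would remove aborted and interrupted tests from the denominator of the completion percentage. Those losses would then show only as a lower attempted count, mixed with tests never launched. SAP 5.7 is the only definition of attempted in the two documents. The derivations are held elsewhere ("The Specification Document that describes the Analyses dataset variables is" a separate file, which is not in the documents), so the programmed rule cannot be checked.

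**Working it through.** **Plan's own figure.** The disputed rules carry no stated figure. The sample size reproduces. With the exact one-sided binomial test at n = 231, H0 is rejected at 217 or more successes, with type I error 0.0239 at 90% and power 0.816 at 95%. Then 231/5 rounds up to 47, and 47/(1 − 0.2) = 58.75 rounds up to 59. The primary rate divides successes by completed tests with a manual value, so neither issue touches it.

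**(a) Ceiling in 10.2 and 10.3.** If every IS4 subject is tested on an IS4-only vector and has a manual value, attempted % = (IS4 subjects in EP)/(EP). The documents do not give the IS4 share. EP sizes of 59 (enrolment target) and 47 (target for analysis) are assumptions. The SAP 10.2 colours are orange below 75%, brown from 75% to 90%, and green above 90%.

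| Assumed EP | Highest orange | Lowest brown | Highest brown | Lowest green |
|---|---|---|---|---|
| 59 | 44/59 = 74.6% | 45/59 = 76.3% | 53/59 = 89.8% | 54/59 = 91.5% |
| 47 | 35/47 = 74.5% | 36/47 = 76.6% | 42/47 = 89.4% | 43/47 = 91.5% |

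Full testing of IS4 subjects is therefore coloured orange unless at least three quarters of EP have an IS4 lead.

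**Limit from the manual-data restriction.** CIP 6.1.2 schedules manual tests at M0 on LV2-LV4, LV3-LV4, LV3-LV2 and LVtip1-LV4. CIP 6.1.3 schedules them at M1 on LV3-can, LV3-RVring, LV3-RVcoil and LV4-RVcoil. Further manual tests are optional. At each visit, four of the eight IS4-only vectors therefore have no scheduled manual test. LVtip-RVring is the sixth common vector in SAP Table 2 but is not among the five common vectors listed in CIP 4.1.2. Such cells can stay below 100% even with the right lead denominator.

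**(b) Two readings of attempted.** Let a be the share of launched tests aborted or interrupted, and v the share that run through but return no value. The documents give neither for this algorithm.

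- Launch rule: completed/attempted = 1 − a − v.
- *That is* rule: completed/attempted = (1 − a − v)/(1 − a), larger by the factor 1/(1 − a).

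The factor is 1/0.95 = 1.05 at a = 5%, 1/0.89 = 1.12 at 11%, and 1/0.80 = 1.25 at 20%. For illustration, take 78% completion under the launch rule (the completion figure that the literature table in CIP 2.2.1 gives for another manufacturer's quadripolar-lead algorithm):

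| a | v | Launch rule | *That is* rule | Colour under *That is* rule |
|---|---|---|---|---|
| 5% | 17% | 78% | 78/95 = 82.1% | brown |
| 11% | 11% | 78% | 78/89 = 87.6% | brown |
| 20% | 2% | 78% | 78/80 = 97.5% | green |
| 22% | 0% | 78% | 78/78 = 100% | green |

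The launch-rule cell is brown throughout.

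For 11.1C, assume 5 tests with unexpected function per 100 launched, none of them aborted or interrupted. The 5% becomes 5/95 = 5.3% at a = 5%, or 5/80 = 6.3% at a = 20%. If some of the five were aborted or interrupted, the numerator could change too.

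In 10.4B the denominators are subjects, so only the Attempted distribution would change.

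**The case against.** **The SAP settles the meaning of attempted.** The first sentence is a two-way split on launch, two Table 3 rows agree with it, and the text says the table clarifies the conditions. Read as strict logic, the *That is* sentence gives only a sufficient condition and never calls an aborted test not attempted. This largely stands: the launch rule is better supported, and harm needs the sentence to be programmed against the rest of 5.7. What remains is that *That is* announces a restatement, and read so it is wrong.

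**The manual-data line may already remove IS1 subjects.** An IS1 subject has no manual value on an IS4-only vector, and 5.7 speaks of an available vector. But 10.2 does not say the restriction works vector by vector, and it then names EP as the denominator without qualification. The restriction does not override that statement.

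**The figures are not data from this trial.** That is right. They show direction and range only.

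**A reader might infer more than the documents support:**

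- That the lead-specific denominator would show 100% whenever all IS4 subjects are tested. In 10.2 and 10.3 the manual-data restriction can still hold cells lower.
- That reported completion is inflated, or is 100% by construction. The programmed rule cannot be seen, and the 5.7 text keeps no-value tests as attempted but not completed.
- That the missing Table 3 row is a gap in the rules. The text supplies the rule, so only the table is incomplete.

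**Conclusion.** The point holds, as a minor one, in two parts of unequal weight.

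The denominator in 10.2 and 10.3 is wrong as written. Following it caps the attempted percentage of the eight IS4-only vectors at the IS4 share of EP, and it departs from the lead-specific rule used elsewhere in the SAP. The size depends on an IS4 share that the documents do not give. A reader could recover lead-specific attempted percentages from 11.1B, which reports both visits.

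The *That is* sentence in 5.7 conflicts with the sentence before it and with Table 3. Its effect is conditional: only if it is programmed is completed/attempted inflated by 1/(1 − a) in 10.1 to 10.3, 11.1B and 11.1C.

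All affected outputs are descriptive. The primary test, the 231/47/59 sample size, and the successful and accurate percentages stand. Confidence is high on the textual mismatches; the numerical effects rest on assumed abort rates, EP sizes and IS4 shares.

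**What to change.** 1. **SAP 10.2 and 10.3:** for the eight IS4-only vectors, take the attempted percentage on EP subjects with an IS4 lead. Keep EP for the six common vectors.
2. **Footnote to those tables and heat plots:** the non-missing-manual restriction can keep cells below 100% for vectors with no scheduled manual test at that visit. These are four of the eight IS4-only vectors at each visit (a different four at M0 and M1), and LVtip-RVring.
3. **SAP 5.7:** delete the *That is* sentence, so that attempted means launched whatever the outcome. Check that the derivation specification follows this.
4. **Table 3, editorial only:** add the row Attempted Yes, Aborted No, Interrupted No, Complete No, Threshold Value Missing.

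The cost is one denominator, one footnote, one deleted sentence and one table row, recorded in the SAP change history. No new data are needed. If the deleted sentence would otherwise have been programmed, completion percentages will look less favourable.

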7. RISK ANALYSIS

7.1. POTENTIAL & RESIDUAL RISKS

The risk analysis and the risk mitigation of the investigational feature are detailed in the Investigator Brochure (Appendix A). The main risks include the following:

- Anodic stimulation or fusion leading to under-estimation of the pacing threshold
- Inappropriate or absence of back up pacing leading to long ventricular cycle
- Slow VT detection temporarily turned off during the test leading to inability to detect Slow VT during the test

These risks are all mitigated by design and are considered acceptable.

The Global Product Analysis of the device supporting the feature under investigation (Ref. AR00523 and AR 00503) did not identify any significant additional risk related to device use.

The procedures required by the CIP do not differ from routine follow-up practice, except for the launch of the "In-Clinic LVAT" tests which is not expected to lead to other risks than the ones associated to standard threshold pacing tests.

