2.3. SAMPLE SIZE CALCULATION

The study primary objective will be met in case the null hypothesis that the success rate of the “In-Clinic LVAT” is lower than 90% is rejected.

The following assumptions were made to calculate the sample size:

- Power = 80%
- One-sided alpha = 2.5%
- Null Hypothesis proportion of success-rate (target) = 90%

LEVEA – Statistical Analysis Plan

- Expected success-rate = 95%

With these assumptions, it is required to carry out at least 231 LV vector tests. As we will have 5 different pacing vectors for each subject, we will need 47 ($\sim 231/5$) subjects.

An attrition rate of 20% is expected for this study.

Thus the number of subjects needed to be enrolled to obtain 47 evaluable subjects = $47/(1-0.2) = 59$ subjects.

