9. PRIMARY EFFICACY ANALYSES

9.1. PRIMARY ENDPOINT ANALYSIS

9.1.1. PRIMARY ENDPOINT

The primary endpoint of the study is the success rate of “In-Clinic LVAT” test, that is the (Number of successes/Total Number of completed LV vector tests excluding the tests for which Manual tests are missing) of the “In-Clinic LVAT” feature.

For the primary endpoint, the evaluation is performed on 5 LV pacing vectors common to IS1 and IS4 leads:

Table 7: LV tests for Primary Endpoint

#	IS1 lead	IS4 lead
1	LVtip-LVring	LVtip1-LV2
2	LVtip-RVcoil	LVtip1-RVcoil
3	LVtip-CAN	LVtip1-CAN
4	LVring-RVcoil	LV2-RVcoil
5	LVring-CAN	LV2-CAN

Test will be evaluated at different LV pacing conditions: DDD A-test and VVI test. Among all the eligible complete LV Vector Tests collected, only those performed in DDD A-test with atrial overdrive pacing configuration (if available, otherwise in VVI) and with a manual LV threshold test performed in the same conditions (same pacing pulse width) and reported in the electronic Case Report Form (eCRF) will be retained. In case several LV Vector Tests were eligible with the same LV pacing vector, for the same subject, on 2 different visits, only M0 data will be considered.

The primary analysis is based on manual tests which are non-missing and for which complete LV Vector Tests are provided by the algorithm and collected at M0. If data at M0 is unavailable, then corresponding data collected at M1 will be considered.

To summarise, the following table mentions the adequate LV pacing configuration to be considered for the LV Vector test for the Primary Analysis:

Table 8: LV tests for Primary Analysis

Cases	Visit	LV pacing Configuration		Which one to use?
		DDDA-test	VVI test	

LEVEA – Statistical Analysis Plan

Cases	Visit	LV pacing Configuration		Which one to use?
		DDD-test	VVI test	
Case 1	M0	Available	Available	Use DDD A-test
Case 2	M0	Available	Unavailable	Use DDD A-test
Case 3	M0	Unavailable	Available	Use VVI test
Case 4	M0	Unavailable	Unavailable	Go to M1
	M1	Will be considered only for Case 4		
Case 5	M1	Available	Available	Use DDD A-test
Case 6	M1	Available	Unavailable	Use DDD A-test
Case 7	M1	Unavailable	Available	Use VVI test
Case 8	M1	Unavailable	Unavailable	Unavailable

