11. SECONDARY SAFETY ANALYSES

11.1. ASSESSMENT OF THE DEVICE CHARACTERISTICS IN TERMS OF SAFETY AND DEVICE DEFICIENCY

- A. Serious adverse device events and device deficiencies will be collected during each subject visit. Confirmation of absence of USADE during “In-Clinic LVAT” tests will be evaluated by analyzing all SAEs and device deficiencies (DD) collected at each visit.

This secondary endpoint will be based on IP.

- B. Algorithm characteristic: Underestimated Assessments

Assessment of LV pacing threshold underestimation: comparison to manual LV threshold value will be performed by comparing manual and automatic LV threshold values at each visit. An underestimated LV threshold value of “In-Clinic LVAT” feature is defined as a value result more than 2 steps below the LV threshold measured manually (meaning -0.5V if threshold<2.5V, else -1V as measured) . Please see table 6.

LEVEA – Statistical Analysis Plan

Number and percentages of “underestimated” assessments will be presented along with the exact 95% CI (Clopper & Pearson, 1934) by M0 and M1 visit. Only subjects with non-missing manual data will be considered.

The reasons for LV pacing threshold underestimation at M0 visit will be presented as table and listing. The missing reasons (if any) for underestimation will be presented as “Not available”. For the table, the number and percentages of the reasons will be presented with the denominator of the percentages based on the total number of LV pacing threshold underestimated.

Total number of attempted, completed,, Underestimated LV vector tests will be presented by LV vector for each LV pacing configuration by visit.

For the LV tests performed for patients with either IS1 and IS4 leads (six LV vectors common to IS1 and IS4) , the percentage for the number of LV vector tests “attempted”, will be calculated based on the number of patients implanted with either IS1 and IS4 leads.

For the LV tests performed for patients with IS4 leads (eight LV vectors pertaining only to IS4), the percentage for the number of LV vector tests “attempted”, will be calculated based on the number of patients implanted with IS4 lead.

For number of LV vector tests “completed”, the percentage will be calculated based on the number of LV vector tests attempted.

For number of LV vector tests “Underestimated”, the percentage calculated based on number of Complete LV vector tests .

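### A manual threshold test that was done but has no value is set to 'Missing' and excluded, so a manual no capture recorded without a value would drop out of both the primary and the underestimation comparison

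*SAP*

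**What the plan says.** SAP 5.7 treats the two sides of the comparison differently.

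- **Algorithm.** A result of no capture, or a threshold above 5 V, "at starting amplitude is considered as a complete LV Vector test". It carries a value that Table 4 can score.
- **Manual test.** Tables 4 and 6 list manual values from 0.25 V to 7 V and have no row for no capture. The note under each says that "if an LV test is reported to be done, but no manual threshold value is present, it will be imputed as" 'Missing'.
- **Independent reviewer.** Table 5 has a >5 category, and SAP 10.1 scores agreement on >5 V as accurate.

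The 'Missing' status then decides what is analysed. The primary denominator in SAP 9.1.1 is the "Total Number of completed LV vector tests excluding the tests for which Manual tests are missing", and 9.1.2 repeats this. SAP 10.2 keeps only tests with a reported manual result, and 10.3 follows 10.2. For underestimation, SAP 11.1 B says: "Only subjects with non-missing manual data will be considered".

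Protocol 7.1 opens its list of main risks with "Anodic stimulation or fusion leading to under-estimation of the pacing threshold", and Protocol 4.1.3 e makes underestimation part of the safety assessment.

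**The concern.** A manual test that never captures is a performed test without a threshold, so it fits the wording of the note. Suppose the physician finds no capture on a vector and the algorithm returns 2.0 V. The algorithm has then declared capture where the comparator found none, which is an extreme form of the risk named in Protocol 7.1. Read literally, the SAP counts this pair neither as a failure in the primary endpoint nor as underestimated in 11.1 B. A pair in which both methods find no capture is lost as well, although it would be a success.

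The exclusion would therefore depend on the comparator's result and not on whether the test was carried out. It affects the denominator of the confirmatory test and a safety endpoint.

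**Working it through.** **Inputs.** SAP 2.3 gives "One-sided alpha = 2.5"%, "Null Hypothesis proportion of success-rate (target) = 90"%, "Expected success-rate = 95"%, 80% power, 231 tests, 5 vectors per subject and 20% attrition. The test is the exact one-sided binomial of SAP 9.1.2, with tests treated as independent, as the plan does. The documents do not give the share of manual tests without capture or the false-capture rate among them. Both are assumed below.

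**1. The plan's own figures.** The smallest x with P(X ≥ x | 231, 0.90) < 0.025 is 217, with exact size 0.0239. Power is P(X ≥ 217 | 231, 0.95) = 0.816. Then 231/5 = 46.2, rounded up to 47, and 47/0.8 = 58.75, rounded up to 59. The stated sample size is reproduced and is not in question.

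**2. What happens to each kind of pair.**

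| Manual | Algorithm | Primary (Table 4) | Underestimation (Table 6) |
|---|---|---|---|
| 7 V | 2.0 V | failure | underestimated |
| 6 V | 2.0 V | failure | underestimated |
| done, no value | 2.0 V | excluded | excluded |
| done, no value | >5 V | excluded | excluded |

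Only pairs without a manual value are affected.

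**3. How few pairs matter.** Restore k excluded false captures as failures and no concordant pairs.

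- From 217/231 (p = 0.0239), k = 1 gives 217/232, p = 0.040: the claim is lost.
- From 219/231 (p = 0.0063), k = 2 gives 219/233, p = 0.0217; k = 3 gives 219/234, p = 0.037: the claim is lost.
- If 10 concordant pairs are restored together with those 3 false captures, the result is 229/244, p = 0.0232: the claim stands.

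**4. Direction and size.** Let q be the share of all pairs with manual no capture and g the false-capture rate among them. If the true rate over all pairs is 0.90, the rate r among retained pairs satisfies 0.90 = (1 − q)r + q(1 − g), so

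r = [0.90 − q(1 − g)]/(1 − q).

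With q = 0.05:

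- g = 0.10: r = 0.855/0.95 = 0.9000
- g = 0.25: r = 0.8625/0.95 = 0.9079
- g = 0.50: r = 0.875/0.95 = 0.9211

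The chance of claiming success, P(X ≥ 217 | 231, r), over an assumed range of q is:

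| q | g = 10% | g = 25% | g = 50% |
|---|---|---|---|
| 2% | 0.0239 | 0.0335 | 0.0570 |
| 5% | 0.0239 | 0.0555 | 0.1822 |
| 10% | 0.0239 | 0.1265 | 0.6955 |

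At g = 10%, which equals the overall failure rate, the exclusion is neutral. Above that the type I error rises; below it, the rule works against the sponsor. At the plan's expected 95% success rate the neutral point is 5%.

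**5. Upper limit.** If a fraction f of all pairs are excluded false captures and no concordant pairs are excluded, r = 0.90/(1 − f). For f = 1%, 2% and 3% this gives r = 0.9091, 0.9184 and 0.9278, and a false-claim risk of 6.3%, 14.6% and 29.9%. If a fraction c of all pairs are also excluded but concordant, r = (0.90 − c)/(1 − f − c). At f = 2% the risk falls from 14.6% (c = 0) to 6.3% (c = 10%) and 2.4% (c = 18%).

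**The case against.** The strongest reply is that the note never mentions no capture. It also covers a value that was measured but not entered, and for that case 'Missing' is right. The eCRF might code no capture as a number, or as a failed measurement, a category that appears in SAP 17.6 (there only as a reporting convention, without a scoring rule). This stands: that no capture is left blank is an inference. It is also why the rule has to be written down.

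Three stronger readings are tempting, and the documents do not support them.

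- *The primary success rate is necessarily biased upward.* Concordant pairs are dropped too, so the direction depends on the mix, which is unknown.
- *False capture in general escapes both endpoints.* Against any numeric manual value, including 6 V and 7 V, an algorithm value outside the Table 4 range is a failure, and one below the Table 6 limit is underestimated.
- *The risks of 6%, 15% and 30% in step 5 are estimates.* They set concordant pairs to zero and are upper limits for each f.

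The plan also has partial safeguards. SAP 10.1 and 13.1 compare the algorithm with the reviewer at M0 without needing a manual value, so they would show these false captures. SAP 9.1.2 lists all LV vector test results, and Protocol 9.1 provides for queries on omissions. For the primary endpoint, M1 data may stand in for M0 data treated as unavailable, so the vector may not be lost; the text does not say whether a done-but-valueless manual test triggers this. None of these replaces the manual comparison on which the primary and underestimation endpoints rest. The tipping-point analysis in SAP 9.1.3 runs only if fewer than 231 tests are completed and the null hypothesis is rejected.

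**Conclusion.** The point holds in a conditional form. The SAP excludes every performed manual test without a value and has no place in Tables 4 and 6 for a manual no capture, although it scores that state for the algorithm and the reviewer. If such results are recorded without a value, the underestimation endpoint misses every discordant pair of this kind. The primary rate is inflated only where the false-capture share among dropped pairs exceeds the failure rate among retained pairs.

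The possible size is material. One restored false capture overturns a result at the rejection boundary, and three overturn 219/231 if no concordant pairs return with them. With 5% of pairs affected, the false-claim risk runs from the nominal 2.4% to 18% as false capture rises from 10% to 50%. These figures rest on assumed frequencies and on independence between tests. They show what the rule could do, not what it did.

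**What to change.** 1. In SAP 5.7, limit 'Missing' to manual tests that were not performed or whose result was not recorded, and state how the eCRF codes manual no capture.
2. Add a row for no capture at the maximum tested output to Tables 4 and 6: success if the algorithm gives >5 V; failure, and underestimated, if it gives 5 V or less. Record that maximum output with the result, because the row presumes that the manual test reached the algorithm's 5 V starting amplitude (SAP 13.1).
3. Query every performed manual test without a value, using the site record and the printed report file, to separate no capture from an unrecorded value.
4. Keep and list the no-capture pairs in 9.1.1, 9.1.2, 10.2, 10.3 and 11.1 B, and say whether M1 may replace such a pair at M0.
5. Report the number of pairs still excluded for lack of a manual value.

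The cost is SAP wording, one row in each of two tables and some data queries. The reported success rate may be slightly lower. The change concerns scoring only and alters no test procedure.
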